THE IRB MUST BE NOTIFIED OF COMPLETION OF THIS STUDY.....	32

REFERENCES	33
TABLES.....	34
TIMELINE AND EVENTS SCHEDULE.....	34
STUDY SCALES AND ASSESSMENTS.....	35

INVESTIGATOR'S STATEMENT OF AGREEMENT

I have read the foregoing protocol and agree that it contains all necessary details for conducting the study. I will conduct the study as outlined herein and will complete the study within the time designated.

I agree to conduct this protocol in accordance with local regulations, external standards and applicable ICH and Good Clinical Practice (GCP) guidelines.

I will provide copies of the protocol, including any amendments, and all pertinent information to all individuals responsible to me who assist in the conduct of this study. I will discuss this material with them to ensure they are fully informed regarding the ZELTIQ Aesthetics, Inc. device and the conduct of the study.

I further agree to provide access to ZELTIQ Aesthetics Inc, its designees, or regulatory authorities to any source documents from which case report form information may have been generated.

I agree to maintain the confidentiality of all information received or developed in connection with this protocol.

Principal Investigator
(Print name)

Principal Investigator
(Principal Investigator's signature)

Date

[figure not shown]
CLINICAL SITE

STUDY SYNOPSIS

Purpose	The purpose of this single-site clinical study is to evaluate the safety and effectiveness of three (3) treatments sessions with the ZELTIQ Aesthetics, Inc. Rapid Acoustic Pulse (RAP) device for the improvement in the appearance of cellulite.
Primary Effectiveness Objective	
 • RAP treatment effectiveness: The primary effectiveness objective will demonstrate improvement in the appearance of cellulite as determined by correct identification of baseline vs 12-weeks post final treatment images [REDACTED] [REDACTED] by at least 2 of 3 blinded independent physician reviewers (IPR).
Primary Safety Objective	
 • RAP treatment safety: The primary safety objective is to evaluate the safety of the RAP (Rapid Acoustic Pulse) device for cellulite treatments through the monitoring of the incidence of adverse events (AEs) and adverse device effects (ADEs); serious adverse events (SAEs) and SADEs (serious adverse device effects) and pain assessments.

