Secondary Effectiveness Objective	
 • RAP treatment effectiveness: The secondary effectiveness objective is to demonstrate the improvement in the appearance of cellulite as determined by the study participants selecting “Agree” or “Strongly Agree” as answers to the Participant Satisfaction Survey (Assessment 3): when comparing side-by-side before and after photographs.
Test Device	ZELTIQ Aesthetics, Inc. Rapid Acoustic Pulse (RAP) device.
Treatment	
Each cellulite treatment session will consist of RAP treatment [REDACTED] to bilateral thigh and/or buttock areas using the same treatment settings for both sides.
 
The participants will have three (3) separate cellulite treatment sessions. The second treatment session will occur four (4) weeks post the initial treatment. The third treatment session will occur twelve (12) weeks post the second treatment.

Control	For each cellulite treatment area, the pre-treatment photos of the thighs and/or buttocks area will serve as a control.
Study Design	Non-significant risk, single-site, prospective clinical trial.
Planned Number of Sites / Countries	One clinical trial site located in the United States.

Planned Duration of Participant Engagement	Up to seventy-two (72) weeks [REDACTED]
Planned Number of Participants/ Treatment Areas	Up to 15 participants [REDACTED] (total of two thighs and/or buttocks per participant) The clinical site (CS) will recruit up to 15 participants. This will provide a total of up to thirty treatment areas.
Primary Effectiveness Endpoint	
 Effectiveness Endpoint: An Independent Photo Review (IPR) panel will be asked to identify the 12-weeks post final treatment photographs from randomly placed side-by-side before and after photographs, for all participants who meet all the inclusion criteria and none of the exclusion criteria and complete the 12-weeks follow-up visit. The number of before and after photos correctly identified by at least 2 of 3 blinded reviewers from the IPR panel will be recorded. [REDACTED]
Primary Safety Endpoint	
 RAP treatment safety endpoint: To demonstrate safety through the absence of unexpected adverse events (UAEs) and serious adverse events (SAEs) directly attributable to the RAP device or treatments.

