Short-term (12-week) analysis was conducted in fifty-six participants who completed a full treatment of the identified treatment areas and who completed the 12-week follow up visit. Serial clinical photographs were collected before RAP treatment under standardized conditions at the baseline (0-week) visit and at the short-term (12-week) follow-up visits. Photographs were assessed by blinded independent reviewers (IPR) to correctly identify the 12-weeks post-treatment photographs from randomly placed side-by-side comparison of before and after photographs. Additionally, the IPR graded the pre-treatment and post-treatment images using the simplified 6-point Cellulite Severity Scale (CSS) [3] and improvement using the Global Aesthetic Improvement Scale (GAIS). Safety assessments included evaluation of Adverse Events (AEs) via physician examination during and after the treatment.

[figure not shown]
The short-term (12-week) results demonstrated that a single non-invasive acoustic subcision session can safely provide meaningful improvement in the appearance of cellulite in terms of depressions with minimal treatment pain and no post-treatment down time. The post-treatment photographs were correctly identified by blinded IPR from randomized pairs of pre/post-treatment photographs at a rate of 96.4%. Furthermore, the participants had a mean CSS reduction of 1.01 (a 29.5% reduction from baseline). Cellulite was graded as improved, much improved, or very much improved using the GAIS at 90.9% of treated locations. Finally, 92.9% of participants reported positive satisfaction responses. No device related unexpected or serious AEs were noted at treatment or follow-up. Overall average pain score during treatment was 2.4 (0-10 pain scale) and 0.3 immediately post-treatment.

[figure not shown]

Protocol 2021-06 Study Objectives and Endpoints

Primary Objectives	Primary Outcome Endpoints
RAP treatment effectiveness: The primary objective is to demonstrate improvement in the appearance of cellulite by blinded independent physician reviewers (IPR).	Effectiveness Endpoint: An IPR panel will be asked to identify the 12-weeks post final treatment photographs from randomly placed side-by-side before and after photographs, for all participants who meet the all inclusion criteria and none of the

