	
exclusion criteria and complete the 12-week follow-up visit. The number of before and after photos correctly identified by at least 2 of 3 blinded reviewers from the IPR panel will be recorded.
 
[REDACTED]

RAP treatment safety: The primary objective is to evaluate the safety of the RAP device for cellulite treatments.
	
RAP treatment safety endpoint: The numbers and proportions of participants with AEs, SAEs, ADEs, SADEs, and unanticipated AEs or ADEs will be summarized.
 
RAP treatment safety: The safety objective is to evaluate the safety of the RAP (Rapid Acoustic Pulse) device for cellulite treatments through the monitoring of the incidence of adverse events (AEs) and adverse device effects (ADEs); serious adverse events (SAEs) and SADEs (serious adverse device effects) and pain assessments.

Secondary Objectives	Secondary Outcome Endpoints

RAP treatment effectiveness: The secondary objective is to demonstrate the improvement in the appearance of cellulite as determined by the study participants.
	
For all participants who meet all inclusion criteria and none of the exclusion criteria and are followed up at the 12-week timepoint post final treatment,
 
[REDACTED]
 
[REDACTED]
 
In comparison to the pre-treatment photo, the 12-week photograph of the treatment area appears improved.

STUDY DESIGN

This is a non-significant risk, single-center, prospective trial for safety, and effectiveness using ZELTIQ Aesthetics, Inc.'s RAP device for the improvement in the appearance of cellulite performed at 1 clinical research site in the United States.

Up to fifteen (15) healthy participants between the age of 18-50 will be enrolled in this study.

Participants who sign the informed consent form and meet all the eligibility criteria will be enrolled in the study. Each participant will undergo acoustic rapid pulse (RAP) treatments on both of their thighs and/or buttocks.

Total study duration is anticipated to be at or less than 72 weeks from the first participant visit to the last participant observation visit. A total of up to 7 visits are planned for this study [REDACTED].

Selection of Study Population

The clinical study can fulfill its objectives only if appropriate participants are enrolled.

The following criteria are designed to select participants for whom protocol requirements are considered appropriate.

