Participants who meet all inclusion criteria and none of the exclusion criteria will be enrolled in the study and assigned a participant No./ID in sequential order (i.e., 01, 02, 03, etc.)

[figure not shown]
Inclusion Criteria

- Healthy candidates ages 18-50 years
- Seeking treatment of cellulite in the thigh and/or buttock areas
- Areas of moderate to severe cellulite on bilateral thigh and/or buttock using the Cellulite Dimple – At Rest Scale at Baseline with grades of 2 or 3 based on review of photos taken under the same lightening conditions planned for the trial.
- Participant will not have had minimally invasive, invasive or energy-based cellulite (liposuction, subcision, RF, laser, ESWT, cryo-lipolysis, muscle stimulation, etc.) treatments in the treatment areas in the prior 12 months.
- Participant will not have used topical based cellulite treatments for prior 3 months and will not use during the trial.
- Participant will not have used spray-on tanning treatments for 3 months prior to or during the term of the trial.
- Participant must be able to provide written informed consent, understand and is willing to comply with all study-related procedures and follow-up visits.

Exclusion Criteria

- Participant is unwilling to have research photos and/or videos taken of treatment areas in the presence of Sponsor's research team.
- Participant is unwilling to have RAP treatment provided in the presence of Sponsor's research team.
- Participant is pregnant or planning to become pregnant during the duration of the study.
- Participant is unwilling to commit to follow-up visits.

- Metal or plastic implants (vascular stent, or implants in the hips, knees, etc.) in the treatment areas.
- Active electronic implants such as pacemakers or defibrillators.
- History of coagulopathy and/or on anticoagulant medication.
- Skin disorders (skin infections or rashes, psoriasis, etc.) in the treatment areas.
- Medical disorder that would hinder wound healing or immune response
- Any surgical procedure in the treatment areas in the prior 3 months or planned during the duration of the study.
- Any other condition/disease/situation which, as deemed by the PI, would preclude participant from safely participating in or completing the study visits or that may confound study results.

STUDY PROCEDURES

Study procedures as described in this section are outlined in the schedule of assessments.

Study Visits

Visit 1 Baseline Screening and Consent Form (Day -30 to Day 0)

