- Review study procedures, assessments and visit schedule with participants
- [REDACTED]
- Obtain informed consent
- Review of Inclusion/Exclusion criteria
- [REDACTED]
- Fitzpatrick Skin Type Scale (Scale 2)
- [REDACTED]
- Demographics and baseline characteristics (including weight and height)
- Limited physical exam, blood pressure and heart rate
- Review of medical history (3-year history)
- Urine pregnancy test for women of childbearing potential
- Concomitant medication
- 2D Photos of the treatment area
- [REDACTED]

Visit 2 Treatment

Pre-treatment Activities

- Review concomitant medication
- Take vital signs
- Urine pregnancy test for women of childbearing potential
- Adverse event evaluation
- Confirm eligibility
- [REDACTED]
- 2D Photos of the treatment area taken pre and post marking
- [REDACTED]

Note: Visits 1 and 2 may be combined if feasible at time of screening and enrollment.

Treatment

- Administer treatment in accordance with Treatment Recommendations (**See Appendix A, Treatment Recommendations**)

Immediate Post-Treatment Activities

- Adverse event evaluation

Visit 3 Follow Up Visit 4-Weeks Post 1st Treatment (+/- 14 days) and 2nd Treatment

Pre-treatment Activities

- Review concomitant medication
- Take vital signs
- Weight
- Urine pregnancy test for women of childbearing potential
- Adverse event evaluation
- Confirm eligibility
- Collect Diary – Treatment 1
- [REDACTED]
- 2D Photos of the treatment area taken pre and post marking

Treatment

- Administer treatment [REDACTED]

Immediate Post-Treatment Activities

- Adverse event evaluation [REDACTED]

Visit 4 Follow Up Visit 12-Weeks Post 2nd Treatment (+/- 14 days) and 3rd Treatment

- Review concomitant medication
- Take vital signs
- Weight
- Urine pregnancy test for women of childbearing potential
- Adverse event evaluation
- Confirm eligibility
- [REDACTED]
- [REDACTED]
- 2D Photos of the treatment area taken pre and post marking [REDACTED]

Treatment

[figure not shown]
- Administer treatment in accordance with Treatment Recommendations (See Appendix A, Treatment Recommendations)

Immediate Post-Treatment Activities

[figure not shown]
- Adverse event evaluation [REDACTED]

Visit 5 Follow Up Visit 12- Weeks Post 3rd Treatment (+/- 14 days)

[figure not shown]
- Weight
- Review concomitant medication
- Adverse Event evaluation
- [REDACTED]
- 2D Photos of the treatment area

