**Visit 7 Follow Up Visit 52- Weeks Post 3rdTreatment (+/- 14 days)**

[figure not shown]
- Weight
- Review concomitant medication
- Adverse Event evaluation
- 2D Photos of the treatment area

* Local, national, or federal holidays may occur during the timeframe of this study, which may alter the follow up dates.

PHOTOGRAPHY

Baseline photographs will be taken under standardized lighting and equipment settings.

UNSCHEDULED VISITS

An unscheduled visit may be performed at any time during the study at the participant's request or as deemed necessary by the study investigator. The date and reason for the visit will be recorded in the source document.

[figure not shown]
PARTICIPANT WITHDRAWAL AND EARLY TERMINATION

[figure not shown]
Participants may withdraw from the study at any time at their own request or withdrawn from at any time at the discretion of the Investigator for safety, behavioral, or administrative reasons. The Investigator should inquire about reason for withdrawal, request the participant to return for a final visit, and follow up with any unresolved adverse events. The Investigator should notify the Sponsor of any participants withdrawal or discontinuance.

RISKS AND BENEFITS

Clinical Benefit

There is no clinical benefit in this study. The participant may experience an improvement in the aesthetic appearance of the treated areas.

Risk Mitigations

The Investigator in this clinical study has been invited to participate in this study based on his/her previous experience with the use of energy-based systems and other novel modalities in aesthetic dermatology and plastic surgery. Experience with cosmetic treatments is the most critical element in managing participant risk in this trial. All other known risks will be disclosed to the participant via the informed consent process. Risks have been mitigated by the specific design employed in manufacturing the device.

REPORTING ADVERSE EVENTS AND COMPLICATIONS

Adverse Events

The Investigator is responsible for the detection and documentation of events meeting the criteria and definition of an AE or SAE, as provided in this protocol. During the study when there is a safety evaluation, the Investigator or site staff will be responsible for detecting, documenting, and reporting AEs and SAEs as detailed in this Section of the protocol.

At the treatment and follow-up visits, participants will be assessed for known physiological responses and adverse events.

Adverse Event (AE)

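### Does a photography rule that names only baseline photographs leave the primary before/after comparison unprotected?

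*Combined protocol and SAP*

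**What the plan says.** The Study Synopsis defines primary effectiveness through "correct identification of baseline vs 12-weeks post final treatment images", judged correct when two or more of three masked readers agree on the later image. Under Control it adds that "the pre-treatment photos of the thighs and/or buttocks area will serve as a control"; there is no concurrent arm. The secondary endpoint has participants judge the same kind of pair: "In comparison to the pre-treatment photo, the 12-week photograph of the treatment area appears improved".

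The express rule on how photographs are taken is in the PHOTOGRAPHY section: "Baseline photographs will be taken under standardized lighting and equipment settings". The Visit 5 list and Table 1 call for 2D photographs without stating conditions.

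Two other places bear on the matter. The inclusion criteria grade cellulite "based on review of photos taken under the same lightening conditions planned for the trial", which presupposes one lighting arrangement for the trial. The description of the pivotal study says: "Serial clinical photographs were collected before RAP treatment under standardized conditions at the baseline (0-week) visit and at the short-term (12-week) follow-up visits".

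Untreated, unmarked photographs arise at two points: at Visit 1 (up to 30 days before treatment) and at Visit 2, where the list has "2D Photos of the treatment area taken pre and post marking". The two visits may be combined.

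**The concern.** Masking the readers and randomising left/right placement hide the visit label, but not a cue inside the image. If the later photographs differed systematically in camera settings, distance or pose, and readers took that difference for improvement, they would pick the later image correctly with no change in the cellulite. With no concurrent control, nothing in the data would reveal it. The participants' comparison would share the fault.

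Read literally, the rule standardises one member of each pair, which is less than the sponsor reports having done in the pivotal study. The objective also speaks of baseline while the control and secondary endpoint speak of pre-treatment, and no visible text says whether the Visit 1 or the Visit 2 photograph is the before image. At stake would be the meaning of the trial's main result.

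**Working it through.** The plan states no figure to reproduce: the sample size rests on practical considerations, not on power. The check is therefore a reading of the texts, followed by an illustration of what a cue could do.

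**What the visible text leaves open.** Lighting is covered by the inclusion criterion. Equipment settings are named for baseline only. Distance and pose are not mentioned for any visit. Redacted bullets sit beside the photograph items at Visits 1, 2, 4 and 5, the endpoint text is partly redacted, and Appendix A is not in the supplied text.

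**How long the set-up must be held.** The visit list gives 4 + 12 + 12 = 28 weeks from first treatment to Visit 5. Table 1 puts Visit 5 at week 24. (The two schedules need reconciling, but that is a separate matter.) A before image from Visit 1 adds up to 30/7 = 4.3 weeks. The nominal range is about 24 to 32 weeks, before visit windows.

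**Effect of an assumed cue.** Let *q* be the chance that one reader picks the later image through a set-up cue alone, with no improvement. The values of *q* are assumptions.

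- Readers independent: rate = 3*q*² − 2*q*³.
- Readers all respond alike: rate = *q*.

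| *q* | Independent | Alike | Expected correct of 15 |
|---|---|---|---|
| 0.5 | 50.0% | 50% | 7.5 |
| 0.6 | 1.08 − 0.432 = 64.8% | 60% | 9.0 to 9.7 |
| 0.7 | 1.47 − 0.686 = 78.4% | 70% | 10.5 to 11.8 |

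Non-directional variation leaves *q* at 0.5 and the rate at 50%.

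**Would a high observed rate be informative?** The pivotal study's 96.4% applied to 15 pairs is 14.5, so take 14. The exact (Clopper-Pearson) 95% interval for 14/15 is 68.1% to 99.8%. It excludes 60% and 64.8%, that is, both scenarios with *q* = 0.6. Directly, P(at least 14 of 15) = 15*p*¹⁴(1 − *p*) + *p*¹⁵, which is 0.5% at *p* = 0.60 and 1.4% at *p* = 0.648. The scenarios with *q* = 0.7 (70% and 78.4%) stay inside the interval.

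The denominator of 15 is itself an assumption, since the Synopsis counts up to thirty treatment areas. For 29/30 the exact interval is 82.8% to 99.9%, above every scenario in the table. That treats the areas as independent; correlation within a participant would widen it.

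**Which image is the before image.** Only Visit 1 carries the baseline label, in the visit heading and in Table 1. The term pre-treatment is true of both Visit 1 and Visit 2, so the terms do not conflict. Both candidates show untreated skin, and the question disappears when the visits are combined.

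**The case for a change.** The strongest case for a change is that the PHOTOGRAPHY section shows no redaction mark, so the limitation to baseline is the sponsor's own wording. The pivotal study is described more fully, the before photograph is the only control, and an unmatched photograph cannot be repaired later. A longer sentence would cost almost nothing. A strong enough cue could also produce a pivotal-like result: *q* = 0.9 with independent readers gives 2.43 − 1.458 = 97.2%.

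The reading of the sentence stands, and so does the logic of the cue. What does not follow is that the trial is exposed. A directional difference large enough to matter is assumed, not shown. Standardising a baseline photograph has little purpose unless later photographs are to be compared with it, so extending the settings to follow-up is the natural reading. The Synopsis exclusion criteria also require participants to accept photographs taken with, or by, the sponsor's team. That does not prove matching at Visit 5, but with one site and one planned lighting set-up it makes unplanned drift less likely.

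Reporting an exact interval beside the 50% guessing rate has been suggested as an addition. It would neither detect nor remove a photographic cue, and the endpoint and analysis text where such a comparison would appear is partly redacted.

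**Conclusion.** The rule is worded more narrowly than its purpose, and no change to the plan follows. It is a gap in written detail that a single site, with one planned lighting set-up and the pivotal study's practice to follow, would fill sensibly. No set-up difference is shown, and no bias is shown from using either untreated photograph as the before image.

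The possible inflation, from 50% to between 60% and 78%, rests wholly on an assumed per-reader probability of 0.6 to 0.7 acting in the favourable direction. A result near the pivotal rate would exclude the lower part of that range with 15 pairs, and all of it with 30 areas treated as independent. It could not exclude a much stronger cue.

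The conclusion assumes that follow-up photographs are taken under the baseline settings, as the surrounding text indicates. It is limited to the visible text, because the redactions may already contain the matching rule. The study is exploratory and its visible analyses are descriptive, so no formal test depends on this point.

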- AEs will be assigned a relationship (causality) to the study treatment. The Investigator will be responsible for determining the relationship between an AE and the study treatment. The type of event, organ system affected, and timing of onset of the event will be factors in assessing the likelihood that an AE is related to the study treatment. Relationship of AEs to study treatment will be classified as follows:
 - i. Definitely related: This category applies to those AEs that the Investigator feels are incontrovertibly related to the study treatment. An AE may be assigned an attribution of definitely related if or when it meets all of the following criteria: (1) it follows a reasonable temporal sequence from administration of the study treatment; (2) it could not be reasonably explained by the known characteristics of the participant’s clinical state, environmental or toxic factors, or other modes of therapy administered to the participant; (3) it follows a known response pattern to treatment with the study treatment.
 - ii. Probably related: This category applies to those AEs which, after careful medical consideration at the time they are evaluated, are felt with a high degree of certainty to be related to the study treatment. An AE may be considered probable if or when (must have three): (1) it follows a reasonable temporal sequence from administration of the study treatment. (2) It could not readily have been produced by participant’s clinical state, environmental or toxic factors, or other therapies administered to the participant. (3) Disappears or is decreased upon

discontinuation of the study treatment. (4) It follows a known response pattern to treatment with the study treatment.

- iii. Possibly related: This category applies to those AEs which, after careful medical consideration at the time they are evaluated, are judged unlikely but cannot be ruled out with certainty to the study treatment. An AE may be considered possible if or when (must have two): (1) it follows a reasonable temporal sequence from administration of the study treatment. (2) It could not readily have been produced by participant's clinical state, environmental or toxic factors, or other therapies administered to the participant. (3) Disappears or is decreased upon discontinuation of the study treatment. (4) It follows a known response pattern to treatment with the study treatment.

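### The causality scale mixes expectedness with causality, so events outside the known response pattern are graded down and device-attributed counts are biased low

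*Combined protocol and SAP*

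**What the plan says.** The scale is in Reporting Adverse Events and Complications, 3. Causality Assessment.

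- *Definitely related*: "An AE may be assigned an attribution of definitely related if or when it meets all of the following criteria". There are three: reasonable timing, no other reasonable explanation, and "3) it follows a known response pattern to treatment with the study treatment".
- *Probably related*: "An AE may be considered probable if or when (must have three") of four items: timing, no ready alternative explanation, "3) Disappears or is decreased upon discontinuation of the study treatment", and a known response pattern.
- *Possibly related*: "An AE may be considered possible if or when (must have two") of the same four. The grade covers events that "are judged unlikely but cannot be ruled out with certainty to the study treatment".
- *Remotely related*: two of four items. These are timing that does not fit, no ready alternative explanation, disappearance or decrease on discontinuation, and no known response pattern.

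The primary safety endpoint appears in two forms. The Study Synopsis seeks the "absence of unexpected adverse events (UAEs) and serious adverse events (SAEs) directly attributable to the RAP device or treatments". The Study Objectives and Endpoints table says: "The numbers and proportions of participants with AEs, SAEs, ADEs, SADEs, and unanticipated AEs or ADEs will be summarized". An adverse device effect (ADE) is defined as an adverse event related to use of the device. No visible text says which causality grades make an event related or directly attributable.

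**The concern.** Whether an event was foreseen and whether the device caused it are separate questions. The scale answers the second partly with the first. A new kind of device effect is therefore graded lower than a familiar one on the same evidence of timing and lack of other causes, yet unexpected events are what the Synopsis endpoint names first. The discontinuation item adds to this. Treatment is three separate sessions, and after the third nothing is left to stop, but the scale has no option for an item that cannot be assessed.

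At stake are the causality grades, the ADE and serious ADE (SADE) counts that follow from them, and any statement that no attributable unexpected event occurred. The cut-off is open, so it could be chosen after the events are known.

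**Working it through.** The plan gives no figure on this point to reproduce. The check applies the scale to every combination of its items.

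**Inputs** (all from 3. Causality Assessment), each scored 1 or 0: T = reasonable timing; N = not otherwise explained; D = disappears or decreases; K = known response pattern. Two mappings are assumptions: unexpected means K = 0, and non-decreasing means D = 0.

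**Rules**
- Definite: T = N = K = 1
- Probable: T + N + D + K ≥ 3
- Possible: T + N + D + K ≥ 2
- Remote: (1 − T) + N + D + (1 − K) ≥ 2

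**The 8 of 16 combinations with K = 0**

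| T | N | D | Grades whose item count is met |
|---|---|---|---|
| 1 | 1 | 1 | Probable, Possible, Remote |
| 1 | 1 | 0 | Possible, Remote |
| 1 | 0 | 1 | Possible, Remote |
| 1 | 0 | 0 | none |
| 0 | 1 | 1 | Possible, Remote |
| 0 | 1 | 0 | Remote |
| 0 | 0 | 1 | Remote |
| 0 | 0 | 0 | Remote |

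None of the 8 reaches Definite.

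**The two cases that matter most** (T = N = 1, K = 0)
- Event decreases (D = 1): 1 + 1 + 1 + 0 = 3, so the ceiling is Probable.
- Event does not decrease (D = 0): 1 + 1 + 0 + 0 = 2, so Probable fails and the ceiling is Possible. The Remote count is 0 + 1 + 0 + 1 = 2, so that grade fits equally well.

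**Comparison with K = 1.** With T = N = 1 and D = 0, Definite is open. The known-pattern item alone moves the ceiling from Definite to Possible.

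**Remote items that point the wrong way.** An event with T = N = D = K = 1 scores 0 + 1 + 1 + 0 = 2 on Remote while also meeting Definite. Items (2) and (3) of *Remotely related* are worded as in the higher grades, so evidence for a device cause is counted against it.

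**Effect of the cut-off on the Synopsis endpoint**
- Definite only: no event with K = 0 can ever count.
- Definite or Probable: unexpected events that do not decrease are lost.
- Possible included: an unexpected event with T = N = 1 counts, unless it is graded Remote.

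With 15 participants, one re-graded event moves the result from 0/15 to 1/15 = 6.7% and reverses a claim of absence.

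**Effect of the change.** If K is no longer mandatory, T = N = 1 makes Definite available for K = 0, whether D is 1 or 0.

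**The case against.** The strongest reply is that nothing disappears. All adverse events are recorded, all serious ones are reported within 24 hours whatever their cause, and the Safety Analysis section promises a complete listing. The objectives table counts adverse events, serious adverse events and unanticipated adverse events with no causality filter. With at most 15 participants, every unexpected event would be seen individually. This stands. A reader might infer that the scale blinds the primary safety endpoint; the documents do not support that.

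Second, the Synopsis does not equate direct attribution with *Definitely related*, and *Possibly related* is by name a related grade. This also stands: the loss depends on a cut-off that the plan leaves open. But the gap is itself part of the problem, and a listing does not repair it, because the listed grade is the item affected.

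Third, the key terms are undefined. An event could be unexpected in severity or duration yet follow a known type of response. It could then be graded definite even if lasting, since that grade has no discontinuation item. Serious events with a known pattern can be graded definite too. This limits the finding to events outside the known pattern.

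A reader might also infer that any lasting unexpected injury is capped at *Possibly related*. It is not: the item accepts a decrease, so a lasting but improving event can reach *Probably related*. Nor does the share of follow-up after the third session measure the problem (52/68 = 76% from the visit text, 52/64 = 81% from Table 1). It is calendar time, not misgraded events, and an event that fades after the sessions end can be read as meeting the item.

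**Conclusion.** The point holds in limited form. The scale mixes expectedness with causality. An event outside the known response pattern cannot be *Definitely related*. If it also neither disappears nor decreases, it cannot exceed *Possibly related*, even with clear timing and no other explanation, and *Remotely related* fits it equally well. This biases the attribution grade, the ADE and SADE counts, and the Synopsis endpoint towards finding no device cause. It does not hide events, and it leaves the unfiltered counts in the objectives table untouched.

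The size is in grades: none of 8 combinations reaches definite, and the ceiling falls by one step if the event decreases and by two if it does not. The number of events affected cannot be derived from the documents.

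The conclusion rests on reading unexpected as outside the known response pattern, and on the visible text containing no cut-off. The study is small, exploratory and descriptive, so this is a cheap improvement and not a flaw that invalidates it.

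**What to change.** 1. In *Definitely related* and *Probably related*: record expectedness as a separate field, drop the known response pattern as a mandatory item for the first grade, and do not count its absence against the second.
2. In *Remotely related*: remove the lack of a known pattern as support for the grade. Correct item (2), which counts the lack of another explanation as evidence against a device cause. Item (3) has the same reversal and should be corrected with it.
3. Allow the discontinuation item to be marked not assessable, and state how many items each grade then requires. Check that the grades stay in order once items are set aside: if timing and no other explanation suffice for definite, an unchanged three-item rule would make *Probably related* harder to meet than *Definitely related*.
4. State before data review that directly attributable, ADE and SADE include the definite, probable and possible grades.
5. Reconcile the primary safety endpoint in the Synopsis with the version in the objectives table.

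The cost is wording in the protocol and case report form instructions, plus one extra field for expectedness. No visits or participants are added. A few more events may be counted as device-related, so the safety summary may look slightly less favourable.
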